**Purpose of Study**

- The incidence of urinary tract infection (UTI) in women undergoing pelvic floor gynecologic surgery is high, ranging from 10-64% (Falagas, Athanasiou, Iavazzo, Tokas, & Antsaklis, 2008). A recent randomized trial showed that cranberry juice capsules significantly reduced the incidence of UTI in patients undergoing elective gynecologic surgery (19% vs 38%; odds ratio 0.38 with confidence interval 0.19-0.79) (Foxman, Cronenwett, Spino, Berger, & Morgan, 2015).
- Cincinnati Urogynecology Associates, TriHealth Inc incorporated this clinical regimen into their standard practice in early 2016. Currently, all patients who undergo pelvic floor gynecologic surgery and are discharged from the hospital with an indwelling urinary catheter postoperatively are prescribed cranberry juice capsules to reduce the risk of UTI.
- The purpose of this study is to determine if the addition of cranberry juice capsules to our discharge medication regimen for patients discharged home with an indwelling urinary catheter following pelvic floor gynecology surgery reduced the incidence of UTI.
  - **Primary Aim:** To determine the incidence of UTI in patients who were discharged home with an indwelling urinary catheter following pelvic floor gynecologic surgery in those who were prescribed cranberry juice capsules compared to those who were not.
  - **Secondary Aim:** To determine potential risk factors for postoperative UTI, other than urinary catheter use, such as certain demographic and perioperative factors including the following:
    - Age, race, BMI, tobacco use, medical comorbidities, type of surgery performed, type of anesthesia, intraoperative intravenous fluid administration, estimated blood loss, and duration of catheter use.

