### Hypothesis or Research Question

- We hypothesize that the addition of cranberry juice capsules reduced the incidence of UTI in patients discharged home with an indwelling urinary catheter following pelvic floor gynecologic surgery, compared to patients that had similar treatment without cranberry capsules.
- We further hypothesize that the addition of cranberry juice capsules reduced the duration of catheter use for those patients requiring postoperative catheterization following pelvic floor gynecologic surgery.

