### Background

Urinary tract infections (UTI) continue to be one of the most common healthcare-associated infections encountered today (Magill et al., 2012). The majority of these healthcare-associated UTIs are attributed to the use of urinary catheters (Hooton et al., 2010). Unfortunately, urinary catheter use is often unavoidable—as in the setting of postoperative urinary retention (POUR). Generally speaking, POUR can be characterized by any impairment in bladder emptying following surgery (Geller, 2014). Previous research has illustrated that POUR is a particularly common issue following urogynecologic surgery, with incidence rates of 1.4-43% (Dorflinger & Monga, 2001; Hakvoort, Elberink, Vollebregt, Ploeg, & Emanuel, 2004; Partoll, 2002). This means that a substantial number of patients will be discharged from the hospital with urinary catheters, putting them at substantially increased risk of developing a postoperative UTI. From an internal review of previously completed studies, approximately 54% and 25% of patients are discharged with a catheter following pelvic reconstructive surgery and suburethral sling procedures, respectively (Crisp et al., 2016).

The incidence of UTI has been estimated to be 3-4% per year for women in the general population (Foxman, 2014). However, for women undergoing urogynecologic surgery, the incidence of UTI is significantly greater, ranging from 10-64% (Falagas et al., 2008). As alluded to above, this increased incidence is likely related to postoperative urinary catheter use. Other risk factors for postoperative UTI have been postulated including age, menopausal status, history of recurrent UTIs, duration of catheter use, and increased distance between the urethra and anus (Foxman et al., 2015; Sutkin et al., 2010).

Previously, there has been much focus on the use of antibiotics to reduce the incidence of UTI in patients with indwelling urinary catheters. According to the most recent Cochrane Review, there remains limited evidence to indicate that receiving prophylactic antibiotics reduces the rate of bacteriuria and other signs of infection in surgical patients who undergo bladder drainage for greater than 24 hours postoperatively (Lusardi, Lipp, & Shaw, 2013). More recently, the focus of UTI prevention has turned to cranberry capsules.

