Cranberry products are a potential nonantimicrobial method for UTI prevention, as cranberry proanthocyanidins have been shown to inhibit the adherence of P-fimbriated *Escherichia coli* to uroepithelial cells (Howell, Vorsa, Der Marderosian, & Foo, 1998). Because *E coli* is the culprit behind most UTIs, cranberry products remain an appealing UTI prevention strategy. However,

the evidence continues to be conflicting (Jepson, Williams, & Craig, 2012; Juthani-Mehta et al., 2016).

A recent randomized trial published in a high-impact journal showed that cranberry juice capsules significantly reduced the incidence of UTI in patients undergoing elective gynecologic surgery (19% vs 38%; odds ratio 0.38 with confidence interval 0.19-0.79) (Foxman et al., 2015). As a result of this new data, Cincinnati Urogynecology Associates, TriHealth Inc incorporated cranberry capsules into their standard practice as of March 2016. This change was made in an effort to reduce the incidence of UTI in patients requiring urinary catheterization following urogynecologic surgery. Currently, all patients who undergo urogynecologic surgery and are discharged from the hospital with an indwelling urinary catheter postoperatively are prescribed cranberry juice capsules, in addition to the standard discharge medication regimen.

However, the use of cranberry capsules has not been consistently shown to improve these outcomes in other subgroups of patients at risk (Juthani-Mehta et al., 2016). Furthermore, compliance and actual use of the capsules is uncertain, since patients may elect not to fill the prescription or fail to take the medication appropriately.

We aim to determine if the addition of cranberry juice capsules to the discharge medication regimen for patients discharged home with an indwelling urinary catheter following pelvic floor gynecology surgery significantly reduced the incidence of UTI, compared to a separate cohort that did not have cranberry prescribed. Given recent publications, our hypothesis is that the addition of cranberry juice capsules did reduce the risk of UTI. If we determine that cranberry capsules did in fact reduce the incidence of UTI in our study population, we can feel confident in continuing to incorporate this prevention method in our standard practice.

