## Research Plan

- **Study Design**
  - Retrospective chart review
- **Setting for the study**
  - The retrospective chart review will be performed on TriHealth EPIC platform at one of the various clinical locations.
- **Participants**
  - Study population: All women 18 years of age or older, who underwent pelvic floor gynecologic surgery (for the indication of pelvic organ prolapse or stress urinary incontinence) performed by a physician at Cincinnati Urogynecology Associates, TriHealth Inc between April 2015 and September 2015, and April 2016 and September 2016, who required indwelling urinary catheter use upon discharge from the hospital.
  - A chart review will be performed on all patients who underwent pelvic floor gynecologic surgery performed by a physician at Cincinnati Urogynecology

Associates, TriHealth Inc between April 2015 and September 2015, and April 2016 and September 2016 to determine which patients required discharge with an indwelling urinary catheter.

- The charts of those patients who required catheterization postoperatively will be reviewed further and will make up our study population of interest.
- Inclusion criteria
  - Adults 18 years of age or older
  - Underwent pelvic floor gynecologic surgery (for the indication of pelvic organ prolapse or stress urinary incontinence) performed by a physician at Cincinnati Urogynecology Associates, TriHealth Inc between April 2015 and September 2015, and April 2016 and September 2016
  - Required indwelling urinary catheterization upon discharge from the hospital postoperatively
- Exclusion criteria
  - Intraoperative bladder injury, fistula repair, urethral diverticulectomy, or any other need for prolonged catheterization
  - Complications in the 2 weeks following surgery requiring reoperation and subsequent catheter use
  - Allergy to cranberry or its components
  - Failure to present for both the two-week and six-week postoperative office visit
- Sample size
  - Cranberry juice capsules were incorporated into the standard practice of Cincinnati Urogynecology Associates, TriHealth Inc in mid-March 2016. We plan to review six months of data from similar time frames of 2015 and 2016. This will allow us to capture a similar number of patients in the exposure (cranberry juice capsules, 2016) and no exposure (no cranberry juice capsules, 2015) groups.

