  - Given the fact that Cincinnati Urogynecology Associates, TriHealth Inc typically performs 400 surgeries annually, we estimate that reviewing a total of 12 months of data will result in accessing approximately 400 charts.

● **Data Collection**

- Independent variables: cranberry juice capsules prescribed as part of discharge medication regimen
- Dependent variables: UTI as defined by documentation of positive urine culture or treatment by an involved provider, with documentation in the Epic chart within 6 weeks postoperative.
- Each chart will be reviewed and the following data will be collected or extrapolated:
  - General demographic data – Name, date of birth, age, race, weight, height, BMI, parity, tobacco use, medical comorbidities, date of surgery, surgery performed, date of discharge, intraoperative and postoperative

complications, type of anesthesia, intraoperative intravenous fluid administration, estimated blood loss, discharge medications, postoperative urine cultures, prescribed UTI treatment, duration of catheter use, and any postoperative complications or readmissions (fever, ileus, hematoma, transfusion)

- **Intervention or experimental aspect of the study**
  - No intervention will occur as part of this study.
  - There are no potential risks to the study population by any aspect of the study.
- **Statistical Analysis**
  - The primary outcome is the incidence of UTI in patients who were discharged home with an indwelling urinary catheter after pelvic floor gynecologic surgery. To compare the primary outcome between two groups with/without cranberry capsules, the odds ratio and corresponding confidence interval will be utilized. Descriptive statistics will be generated for demographic information such as age, race, BMI, Parity etc. The independent samples t-tests or Mann-Whitney U test will be employed for continuous variables and the Fisher's exact or Pearson Chi-square tests for categorical variables to test any significant difference between two groups. Logistic regression will be implemented to determine potential risk factors for postoperative UTI.

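### The 2015 versus 2016 comparison of UTI reads as an unadjusted odds ratio; a short, prespecified adjusted model would be a cheap improvement

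*Combined protocol and SAP*

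**What the plan says.** The Research Plan sets the groups by period: "exposure (cranberry juice capsules, 2016) and no exposure (no cranberry juice capsules, 2015) groups". Data Collection defines exposure by prescription: "Independent variables: cranberry juice capsules prescribed as part of discharge medication regimen". The Background says that all such patients are now prescribed capsules, so the two definitions should nearly coincide.

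Under Statistical Analysis, directly after the primary outcome is named: "To compare the primary outcome between two groups with/without cranberry capsules, the odds ratio and corresponding confidence interval will be utilized". Descriptive statistics and two-group tests of patient characteristics follow, with no stated consequence if the groups differ. The last sentence reads: "Logistic regression will be implemented to determine potential risk factors for postoperative UTI". That matches the Secondary Aim, whose ten listed factors end with "intraoperative intravenous fluid administration, estimated blood loss, and duration of catheter use" and do not include cranberry.

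The Background names UTI risk factors other than cranberry: "age, menopausal status, history of recurrent UTIs, duration of catheter use, and increased distance between the urethra and anus". The second hypothesis is that "the addition of cranberry juice capsules reduced the duration of catheter use". If the result favours cranberry, the Background concludes that "we can feel confident in continuing to incorporate this prevention method in our standard practice".

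**The concern.** The comparison is between two years of practice. If the 2016 patients differed from the 2015 patients in age, type of surgery or another UTI risk factor, the crude odds ratio would mix that difference with any effect of cranberry. The bias could go either way: a risk factor that became less common in 2016 would look like benefit, and one that became more common would hide benefit.

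The planned group tests might show such a difference, but the plan does not say what would be done about it. An adjusted result could then be added or left out after the data are seen. The stake is the causal wording in the Background, where a lower UTI incidence in 2016 is taken as grounds for confidence in the practice. Most of the data for a short adjusted analysis are already to be collected.

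**Working it through.** **Figures in the plan.** 400 surgeries a year × (6 + 6)/12 = 400 charts, as stated. The cited trial's odds ratio is (0.19/0.81)/(0.38/0.62) = 0.383, as stated (0.38). The plan gives no power or target sample size.

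**Group size.** The Background gives catheter discharge rates of 25% (sling) and 54% (reconstructive surgery). 400 × 0.25 = 100 and 400 × 0.54 = 216, so about 50 to 108 per group if the groups are equal, before exclusions. At the cited 38% and 19%, the pooled UTI count is 50 × 0.57 = 28.5 to 108 × 0.57 = 61.6. A model with cranberry and all ten listed factors, at one parameter each, would have 28.5/11 = 2.6 to 61.6/11 = 5.6 UTIs per parameter. The covariate list must therefore be short.

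**Bias of the crude odds ratio.** All confounder inputs are assumptions: one binary factor, UTI risk 20% without it (odds 0.25), and no cranberry effect. With the factor, risk is 0.25g/(1 + 0.25g), which is 33.3% for a factor odds ratio g = 2 and 42.9% for g = 3. Group risk = (1 − prevalence) × 0.20 + prevalence × risk with the factor.

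Example, g = 3, prevalence falling from 50% to 30%: 0.5 × 0.20 + 0.5 × 0.4286 = 0.3143 in 2015; 0.7 × 0.20 + 0.3 × 0.4286 = 0.2686 in 2016. Crude odds ratio = (0.2686/0.7314)/(0.3143/0.6857) = 0.80.

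The last column is the chance that the Wald 95% interval excludes 1, by exact binomial enumeration at 50 and 108 per group. It is the same for a rise as for a fall.

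| Factor OR | Prevalences | Crude OR, falling / rising | Interval excludes 1 |
|---|---|---|---|
| 2 | 40%, 30% | 0.93 / 1.07 | 4.7% to 5.4% |
| 2 | 40%, 25% | 0.90 / 1.11 | 5.0% to 6.2% |
| 2 | 50%, 30% | 0.87 / 1.15 | 5.5% to 7.2% |
| 3 | 40%, 30% | 0.89 / 1.12 | 5.2% to 6.4% |
| 3 | 40%, 25% | 0.84 / 1.19 | 6.1% to 8.5% |
| 3 | 50%, 30% | 0.80 / 1.25 | 7.2% to 11.2% |
| 2 or 3 | no shift | 1.00 | 4.5% to 4.9% |

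**If cranberry works.** Take a true conditional odds ratio of 0.50 and the strongest scenario (factor odds ratio 3, 20-point shift). The crude odds ratio is 0.65 if the factor rises and 0.41 if it falls. Crude power is exact. Adjusted power is simulated, 5,000 runs per cell, with the factor in the model together with one unrelated covariate (50 per group) or three (108 per group).

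| Per group | Rising: crude / adjusted | Falling: crude / adjusted | No shift: crude / adjusted |
|---|---|---|---|
| 50 | 14% / 27% | 43% / 27% | 26% / 27% |
| 108 | 26% / 53% | 77% / 51% | 52% / 54% |

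Crude power moves with the bias, while adjusted power stays about level. The simulated data held only 23 to 24 UTIs (50 per group) and 50 to 51 (108 per group), fewer than the counts from the cited rates.

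**Accuracy with no cranberry effect** (root mean squared error of the log odds ratio, crude vs adjusted, factor odds ratio 3):
- 15- to 20-point shift: 0.50 to 0.51 for both at 50 per group; 0.35 to 0.38 vs 0.33 to 0.34 at 108.
- 10-point shift: 0.47 vs 0.50 at 50; 0.33 for both at 108.
- No shift: 0.46 vs 0.49 at 50; 0.30 vs 0.32 at 108.

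The adjusted standard error averaged 5% to 10% above the crude one.

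**The case against.** The plan is clearer than it may first appear. A reader might infer that it names no primary estimate. The text does not support that: the odds ratio is attached to the primary outcome and the regression to risk factors, so a crude primary odds ratio is the natural reading. A cranberry term in the regression is possible, since cranberry is the listed independent variable, but nothing states it.

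The design already limits confounding through the same practice, indications, exclusions and calendar months. No document gives a confounder's strength or a shift, and a 15- to 20-point change in one year is a strong assumption. At a factor odds ratio of 2, or with a 10-point shift, the false-exclusion rate is only 4.7% to 7.2%.

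The benefit of adjustment is also conditional. At 50 per group it does not improve accuracy when cranberry has no effect. If the shifting factor is left out of the model, power in the rising case is 14% and 27%, essentially the crude figures. Menopausal status and recurrent UTI, both named in the Background, are not named data fields.

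All of this stands, and it limits the size of the point. It does not supply the missing adjustment or say what follows if the groups differ.

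**Conclusion.** The point holds as a cheap improvement. On its natural reading, the primary comparison of two non-randomised yearly cohorts is unadjusted, while the Background would read the result causally. Under the assumed inputs the bias is small to modest: crude odds ratios of 0.87 to 1.15 at factor odds ratio 2, and 0.80 to 1.25 at factor odds ratio 3.

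A reader might infer that a change in case mix could by itself produce an effect as large as the cited 0.38. Nothing in the range examined comes near that. Nor would adjustment make the comparison causal, because a year effect or an unrecorded factor would remain. The case rests on protection against a measured shift in either direction at little cost, and that protection exists only for factors in the model.

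**What to change.** In Statistical Analysis:
- Make the primary estimate the cranberry odds ratio, with its 95% interval, from a logistic regression with a short covariate list. Report the crude odds ratio alongside.
- Fix and rank the list before extraction, from items already collected and measured before discharge, for example age, type of surgery, BMI and one comorbidity.
- Set the number of model parameters from the pooled UTI count after exclusions, counting each level of type of surgery as a parameter.
- Leave catheter duration out of this model. The second hypothesis is that cranberry shortens it, so adjusting for it could remove part of the effect.
- Say whether menopausal status and recurrent UTI will be read under medical comorbidities. If not, list them as unadjusted.
- State that adjustment cannot remove year effects or unrecorded factors, and word the Background's conclusion as an association.

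The cost is a few sentences, a little more analysis work and a standard error about 5% to 10% larger. No new patients are needed and, for the example list, no new data fields.

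### Secondary aim only: Firth fitting of any multivariable UTI risk-factor model, with catheter duration left out of any adjusted cranberry odds ratio, would be a cheap improvement

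*Combined protocol and SAP*

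**What the plan says.** The risk-factor analysis has one sentence, in Research Plan, Statistical Analysis: "Logistic regression will be implemented to determine potential risk factors for postoperative UTI". It gives no fitting method, term list, coding or selection rule. It does not say whether factors are examined singly or jointly, or whether cranberry is in the model.

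The Secondary Aim in Purpose of Study gives ten factors as examples: "Age, race, BMI, tobacco use, medical comorbidities, type of surgery performed, type of anesthesia", then "intraoperative intravenous fluid administration, estimated blood loss, and duration of catheter use".

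Hypothesis or Research Question adds: "We further hypothesize that the addition of cranberry juice capsules reduced the duration of catheter use for those patients requiring postoperative catheterization".

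On size, the Sample size item says "we estimate that reviewing a total of 12 months of data will result in accessing approximately 400 charts". Only women sent home with a catheter are analysed: "The charts of those patients who required catheterization postoperatively will be reviewed further and will make up our study population of interest". Background reports from in-house studies that "approximately 54% and 25% of patients are discharged with a catheter following pelvic reconstructive surgery and suburethral sling procedures, respectively". The exclusions, among them "Failure to present for both the two-week and six-week postoperative office visit", reduce the number further, and no rate is given for them.

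The primary comparison is an odds ratio with its confidence interval, and no covariates are named for it.

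**The concern.** An unspecified logistic regression would normally be fitted by ordinary maximum likelihood (ML). A natural way to meet a ten-factor aim is one model with all ten factors and cranberry. With few events per term, ML exaggerates non-null odds ratios on average, and sparse factors can give separated or extreme fits. Published risk factors would then look somewhat stronger than they are.

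The second problem does not depend on the number of events. On the protocol's own hypothesis, catheter duration lies on the path from cranberry to UTI. Holding it fixed removes the part of any cranberry effect that acts through shorter catheter use. A reader could take that adjusted odds ratio for the effect of prescribing cranberry.

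**Working it through.** **The plan's own figures.** 400 surgeries a year × 12 months of data (two six-month windows) = 400 charts, as stated. The cited trial's odds ratio is (0.19/0.81)/(0.38/0.62) = 0.383, matching the quoted 0.38.

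**Women analysed, before exclusions.** All sling: 400 × 0.25 = 100. All reconstructive: 400 × 0.54 = 216. A 50:50 mix (assumed): 400 × 0.395 = 158. The first two are case-mix extremes.

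**UTIs.** With similar-sized groups and the cited trial's 19% and 38% (assumed to apply here), the mean risk is 28.5%.

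| | N=100 | N=158 | N=216 |
|---|---|---|---|
| Expected UTIs (N × 0.285) | 28.5 | 45.0 | 61.6 |
| Per term, 11 terms (ten factors + cranberry) | 2.6 | 4.1 | 5.6 |
| Per term, 5 terms | 5.7 | 9.0 | 12.3 |

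Other assumptions move the 11-term range. Excluding 20% of women (assumed) gives 2.1 to 4.5. Using 15 terms, because several factors have more than two categories, gives 1.9 to 4.1. The 10% and 64% ends of the incidence range quoted in Background give 0.9-2.0 and 3.3-7.1 (the latter counting women without UTI, the rarer outcome).

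**Bias by simulation.** The 11 assumed terms were: cranberry (true OR 0.383); one binary factor with true OR 2 and 20% prevalence; and null terms (five normal, two binary at 25%, two binary at 10%). There were 6,000 data sets per N. Failed fits, or fits with any coefficient beyond 5 in absolute value, were left out of the bias figures, which favours ML. The five-term model used 12,000 data sets and the one-factor model 20,000.

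| Bias in log odds ratio, away from 0 | N=100 | N=158 | N=216 |
|---|---|---|---|
| 11 terms, OR 2 factor, ML | 13.6% | 8.4% | 4.8% |
| 11 terms, cranberry, ML | 18.7% | 10.2% | 7.2% |
| 5 terms, OR 2 factor, ML | 5.6% | 3.9% | 2.0% |
| 5 terms, cranberry, ML | 9.0% | 5.9% | 3.3% |
| One-factor model, cranberry, ML | 3.8% | 2.0% | 1.5% |

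With Firth the bias is 1.3% or less throughout the 11-term rows and 0.9% or less in the five-term rows. A smaller repeat put Firth as far as 2.7% off for the OR 2 factor at N=100, with Monte Carlo error of 1-2 points. A different assumed set of covariates gave ML bias for cranberry of 21% at N=100 and 7% at N=216, against 2% and 0% with Firth. Excluding 20% of women (N=80/126/173) raises the 11-term ML bias for the OR 2 factor to 20%/11%/7%. Null factors show no material bias.

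**Size beside sampling error.** At N=158 with 11 terms, 0.084 × ln 2 = 0.06, against a standard deviation of 0.52. A true OR of 2 becomes exp(1.084 × 0.693) = 2.12 on average on the log scale.

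**RMSE, OR 2 factor.** At N=158 with 11 terms: about 0.51 with ML and 0.45 with Firth (0.52-0.53 and 0.47 in other runs). With five terms at N=100/158/216: 0.62/0.48/0.40 with ML and 0.56/0.45/0.38 with Firth.

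**Failed or extreme ML fits, 11 terms, N=100.** About 10% with two null factors at 10% prevalence, and about 0.2% when those two are set to 25%. The different covariate set gave 37 of 4,000 (0.9%). The documents give no prevalences.

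**Interval coverage, 11 terms.** ML Wald 95% intervals for cranberry cover 93.4%/94.4%/94.8% at N=100/158/216.

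**Catheter duration.** The inputs are all assumed: gamma-distributed duration with mean 7 and SD 4 days without cranberry, and UTI risks of 38% and 19%. Adding duration to the model moves the total cranberry odds ratio of 0.38 as follows.

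| Odds ratio per catheter day | 1 day shorter | 2 days | 3 days |
|---|---|---|---|
| 1.1 | 0.41 | 0.46 | 0.51 |
| 1.2 | 0.42 | 0.53 | 0.65 |

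**The case against.** The strongest reply is that the plan commits to none of this. A reader might infer an 11-term joint model from the ten-item list, but the list gives examples, cranberry is not on it, and no joint model or adjusted cranberry odds ratio is planned. If factors are examined singly, the bias is minor. This stands, and it is why the point is conditional.

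A reader might also infer that one ML fit in ten will fail. That figure comes from two assumed 10% prevalences and falls to about 0.2% when they are raised to 25%, so only the range can be stated. Nor do the results support a claim that ML intervals are materially too short: profile ML intervals for cranberry covered 91.8% to 94.2%, but Wald intervals were near nominal.

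It can be said that a short term list makes Firth redundant. It does remove much of the bias, but at five terms Firth still lowers RMSE at every N tried. A five-term cap also keeps about half of the named factors out of the joint model, so it is a trade-off and not a requirement.

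Finally, Firth does not cure imprecision, multiplicity or exaggeration among factors picked by significance. With 11 terms and a true OR of 2, the median odds ratio among significant results is 4.7/3.4/2.8 with ML and still 4.0/3.1/2.7 with Firth at N=100/158/216.

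**Conclusion.** The point holds as a low-cost improvement to the secondary aim. If a multivariable model is fitted, ordinary ML overstates non-null log odds ratios by about 5-19% with 11 terms and 2-9% with five, at 100 to 216 women before exclusions. Firth nearly removes this and lowers RMSE. The sizes rest on the assumed 19%/38% risks, the case mix and the assumed factor distributions; the larger figures belong to the all-sling extreme.

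The catheter-duration point follows from the protocol's own text and needs no event count: a model containing both would not give cranberry's total effect. The 0.41 to 0.65 range is only an illustration.

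A reader might go further and conclude that the primary result is at risk. It is not: the documents describe it as an odds ratio without covariates.

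**What to change.** In Research Plan, Statistical Analysis, replace the logistic regression sentence with:

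> Any multivariable risk-factor logistic regression will be fitted with Firth's penalised likelihood, with profile penalised-likelihood 95% CIs, and all terms will be reported as exploratory. Any adjusted cranberry odds ratio will come from a model without duration of catheter use; duration will be examined in a separate model, counting only catheter days before UTI.

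The last clause is there because a UTI may itself prolong catheter use. Fixing a short term list on clinical grounds before data extraction is sensible but optional, since some named factors would then be described only or examined singly. If an expected size is added, state it as about 100 to 216 catheterised women before exclusions.

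Cost: a few lines of text, a standard software option and no new variables. Odds ratios become slightly smaller. With 11 terms, power for a true OR of 2 falls by about one point with profile tests (23.2%/36.4%/44.9% to 22.6%/35.2%/43.8% at N=100/158/216) and by 3-4 points with Wald tests, hence the profile intervals.
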